9 CLINICAL MONITORING STRUCTURE

Monitoring will be performed before, during and after these studies and according to the guidelines provided by the E6 Good Clinical Practice document [24] to ensure that the:

- Rights and welfare of the subjects are respected,
- Data reported from the trial are accurate, complete and verifiable from source documents,
- Conduct of the trial is consistent with the currently approved protocol amendments, with GCP and with applicable regulatory requirements.

9.1 Site Monitoring Plan

Selection and Qualifications of Monitors.

- Monitors will be appointed by the Sponsor,
- Monitors will be appropriately trained so they have the scientific and clinical knowledge necessary to monitor the trial adequately,
- Monitor's qualifications will be documented.

Extent and Nature of Monitoring.

- Sponsor will determine the appropriate extent and nature of monitoring based on the objectives, purpose, design, complexity, blinding, size and endpoints of the trial,
- Sponsor will then ensure that the trial is adequately monitored,
- Monitoring will be performed before, during and after the trial,
- Written documentation can support GCP training, meetings and investigators' qualifications,
- Statistically designed sampling will be used to select the data (specimens) to be verified.

Monitor's Responsibilities.

The monitor should ensure that the trial is conducted and documented properly by:

- Providing the main line of communication between the Sponsor and the Investigator,
- Ensuring that the Investigators have adequate resources and that those resources remain adequate throughout the trial,
- Ensure that the staff and facilities (laboratories and equipment) are adequate to conduct the trial and remain adequate throughout the trial,
- Verify for the investigational product that:
 - Storage times and conditions are acceptable, and supplies are sufficient throughout the trial,
 - Investigational product is supplied only to subjects eligible to receive it and at protocol-specified doses,
 - Subjects are provided with the necessary instructions on properly using, handling, storing and returning the investigational product,
 - Receipt, use and return of the investigational product at the trial sites is controlled and adequately documented,

- Disposition of unused investigational product at the trial sites complies with applicable regulatory requirements and the Sponsor's authorized procedures,
- Verify that the Investigators follow the currently approved protocol and amendments,
- Verify that written informed consent was obtained before each subject's participation in the trial,
- Ensure that the Investigator receives the current Investigator's Brochure and all documents and supplies to conduct the trial properly, and comply with applicable regulatory requirements,
- Ensure that the Investigators and the Investigators' trial staff are adequately informed about the trial,
- Verify that the Investigators and the Investigators' trial staff are performing the specified trial functions in accord with the protocol and other written agreements between the Sponsor and Investigator or Institution, and have not delegated those responsibilities to unauthorized individuals,
- Verify that the Investigators are enrolling only eligible subjects,
- Verify that the Investigators are reporting the recruitment rate,
- Verify that source data and documents are accurate, complete, up-to-date and maintained,
- Verify that the Investigators provide all required reports, notifications, applications and submissions, and that those documents are accurate, complete, timely, legible, dated and identify the trial,
- Check the accuracy and completeness of CRF entries, source data and documents, and other trial-related documents against each other. The monitor should specifically verify that:
 - Data required by the protocol are reported accurately on the CRFs and are consistent with the source data and documents,
 - Any dose or treatment modifications are well-documented for each of the trial subjects,
 - AEs, concomitant medications and intercurrent illnesses are reported on the CRFs in accordance with the protocol,
 - Visits that subjects do not make, and tests and examinations that are not performed are clearly marked (so indicated) on the CRFs,
 - All withdrawals and dropouts from the trial are reported and explained on the CRFs.
- Inform the Investigator about CRF entry errors, omissions or illegibility. The monitor should ensure that appropriate corrections (additions, deletions) are made, dated, explained (if necessary) and signed by the Investigator or an authorized [documented] member of their trial staff,
- Determine whether all AEs are reported within the time periods required by GCP, *ICH Guidance for Clinical Safety Data Management: Definitions and Standards for Expedited Reporting*, the protocol, the IRB/IEC, Sponsor and applicable regulatory requirement,
- Determine whether the Investigator is maintaining the appropriate documents (see *Section 8. Essential Documents for the Conduct of a Clinical Trial*),
- Communicate deviations from the protocol, GCP, SOPs and applicable regulatory requirements to the Investigator and take appropriate actions to prevent recurrence of the detected deviations,

Monitoring Procedures.

The monitor(s) should follow the sponsor's established written SOPs as well as the procedures specified by the sponsor for monitoring a specific trial.

Monitoring Report.

- The monitor should submit a written report to the sponsor after each trial-site visit or trial-related communication.
- Reports should include the date, site, name of the monitor, and names of the Investigators or other individuals contacted.
- Reports should include a summary of what the monitor reviewed and the monitor's statements concerning the significant findings/facts, deviations and deficiencies, conclusions, actions taken or to be taken, and/or actions recommended to secure compliance.
- The review and follow-up of the monitoring report by the sponsor should be documented by the sponsor's designated representative.

10 STATISTICAL CONSIDERATIONS

10.1 Study Outcome Measures

The primary, secondary and tertiary objectives (Section 3, above) and outcome measures (Section 8, above) in this study will be assessed statistically as outlined below (Table 7).

Table 7.

Statistical Assessment of Study Endpoints

COMPONENTS OF THE PRIMARY ENDPOINT

- Lack of recrudescence at 42 days
- < 25% of baseline asexual parasitemia on day 3
- Clearance of asexual parasitemia and fever by day 7

STATISTICAL TESTS

- Pearson χ^2 , Fisher Exact test
- Pearson χ^2 , Fisher Exact test
- Pearson χ^2 , Fisher Exact test

SECONDARY ENDPOINTS

- Adverse Events (AEs) Pearson χ^2 , Fisher Exact test
- Effects on the QT (QTc) Interval (within individuals) Wilcoxon, Friedman test
- Effects on the QT (QTc) Interval (between groups) ANOVA, Kruskal-Wallis test
- Pharmacokinetic Parameters for Parent Compounds (AUC_t, t_{1/2}, Vd/F, Cl/F, MRT) Mann-Whitney, Kruskal-Wallis
- Time to parasite Clearance, Recrudescence or Reinfection (between groups) Kaplan-Meier, Cox Hazard
- Time to fever clearance (between groups) Kaplan-Meier, Cox Hazard

TERTIARY ENDPOINTS

- Pharmacokinetics of metabolites as above
- Aminoquinoline (chloroquine) pruritus Fisher Exact test

AUC_t = total area under the curve; t_{1/2} = elimination half-life; Cl/F = oral clearance; Vd/F = oral apparent volume of distribution; MRT = mean residence time.

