Safety Oversight will be assisted by a Data Safety and Monitoring Board (see section 8.7 on page 33, below).

Flow Chart 2

PROOF OF CONCEPT STUDY FOR AQ-13 ADULT MALES WITH UNCOMPLICATED *P. falciparum* MALARIA

Recruitment in the Villages of Missira and Sirakoroba in Northwestern Mali
and from Outpatient Referral Clinics in the city of Bamako;

In-Patient Studies at the Clinical Research Center, Hôpital Point G in Bamako

Flow Chart 3**PROOF OF CONCEPT STUDY FOR AQ-13
RANDOMIZATION, DRUG ADMINISTRATION AND FOLLOW-UP**

Recruitment in the Villages of Missira and Sirakoroba in Northwestern Mali

and from Outpatient Referral Clinics in the city of Bamako;

In-Patient Studies at the Clinical Research Center, Hôpital Point G in Bamako

EYE EXAMS, HOLTER RECORDINGS, CHEMISTRY PANEL, HEMATOLOGY (CBC)
(n=70; 35 each for the AQ-13 and Coartem groups, expected 5% ineligible).

•INCLUSION CRITERIA:

≥ 2,000 asexual *P. falciparum* parasites per μ l,
Uncomplicated *P. falciparum* malaria,

•Baseline Screening Holter Recording x 1 hour,**•Visual Screening** baseline acuity, visual fields,**•EXCLUSIONS:** Hb ≤ 7 gms/dL, K+ ≤ 3.5 mEq/L, arrhythmias, heart block, BP ≥ 140/90 or severe or complicated malaria.

RANDOMIZE ELIGIBLE ADULT VOLUNTEERS WITH UNCOMPLICATED *P. falciparum* MALARIA
(n=66; 33 each for the AQ-13 and Coartem groups, expected 20% loss to follow-up).

•Filter Paper Blots for molecular studies,**•Freeze Initial Parasites** at -70° C,**•pfcr PCR and other Tests** for CQ Resistance,**•Oral Administration of 700 mg AQ-13 on days 1-2,** followed by 350 mg on day 3, OR

Oral Administration of Coartem, 80 mg artemether

+ 480 mg lumefantrine twice daily x 3 days,

•Repeat Daily Blood Smears (days 1 through 7), repeat Hematology, Chemistry panels on day 4,**•AQ Drug and Metabolite Levels** at 0, 0.5, 1, 2, 4, 6, 12, 18, 24, 24.5, 25, 26, 28, 30, 36, 48, 48.5, 49, 50, 52, 54, 60, 72, 96 and 120 hours x 5 ml,**•Holter Monitoring** 24 hours/day x 4 inpatient days,**•One Week** eye exam, 1 hour Holter recording,**•WITHDRAWAL:** severe or complicated malaria.

FOLLOW-UP
for a total of 6 weeks,
PRIMARY ENDPOINT is
a lack of recrudescence
with the same genotype(s)
(n=28 evaluable subjects/group)

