6.2.1 Laboratory Evaluations/Assays

Subjects who satisfy the first two inclusion criteria (adult Malian males \geq 18 years of age with uncomplicated *P. falciparum* malaria, and 2,000 to 99,999 asexual parasites per μl of blood) will be invited to participate in this study if they fulfill none of the exclusion criteria. Those who accept by providing their informed consent will have 2 additional tubes of blood drawn in Bamako for chemistry and hematology panels (1 each), including glucose-6-phosphate dehydrogenase (G6PD) assays and a separate sample for drug and metabolite blood levels that will also be used to freeze (cryopreserve) malaria parasites for future reference (Flow Chart 4, below on page 26). Laboratory evaluations or assays that will be performed in these studies include:

- Thick smear for asexual *P. falciparum* parasites with quantitative parasite counts (Mali; SOP)
- Filter paper blot for parasite and host genomic DNA (Mali; SOP)
- Rapid (Hemocue) Hb determination for anemia (Mali; SOP)
- Chemistry panel (Piccolo-Abaxis) (Mali; SOP)
- Hematology panel (Coulter A^{CT} 10) for Hb, Hct, WBC, platelets (Mali; SOP)
- Glucose-6-phosphate dehydrogenase (G6PD) determination (Mali; SOP)

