7.1.2 Secondary Outcome Measures

- 1] Adverse Events (AEs) – within 4 weeks of treatment as judged by **blinded** physician reviewers to be possibly related to the study drug(s) using the same criteria as in the Phase 1 study.
- 2] Parasite clearance time – from the initiation of treatment to the first of 2 successive negative smears.
- 3] Time to recrudescence or reinfection – time from the initiation of treatment to the reappearance of asexual *P. falciparum* parasites on the thick smear.
- 4] Effects on the QT (QTc) interval – mean changes from the baseline pre-treatment QT (QTc) interval to the post-treatment QT (QTc) interval after treatment with AQ-13 or Coartem.
- 5] Pharmacokinetic parameters for AQ-13 – these will include measurements of AQ-13 blood levels over time (peak levels, AUC, MRT), drug distribution (Vd/F) and drug elimination ($t\frac{1}{2}$, Cl/F).
- 6] Fever clearance time: Time in hours from the initiation of therapy until disappearance of fever for at least 24 hours.

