7.2 Assessment of Treatment Outcomes

7.2.1 Parasitologic Data

Asexual parasite counts (parasite densities per μl of blood) will be based on the average of two independent readings for each time point – performed by two independent microscopists (both blinded to the treatment the patient received). Blood smears will be obtained beginning at the time of enrollment and continuing twice daily (every 12 hours) until two successive smears are negative during the week-long (6-7 day) inpatient stay. After the patient has been discharged, two thick smears will be obtained at each of the twice weekly follow-up appointments during weeks 2 to 6 (Gantt Chart on page 27).

Laboratory Procedures: Parasite counts will be obtained by examining Giemsa-stained thick blood smears containing a minimum of 300 white blood cells and multiplying the number of asexual parasites observed by 25 to estimate the parasite count based on a white blood cell count of 7,500 white cells per μl of blood.

Quality Control: Slides for which the parasite densities estimated by the two microscopists vary by more than 20% or differ qualitatively (negative vs. positive, presence vs. absence of species other than *P. falciparum*) will be examined by a third senior microscopist to resolve those questions.

Parasitologic Outcomes that will be assessed and compared between the two study arms will include:

- Reduction of asexual parasitemia to < 25% of the admission parasite count by day 3,
- Clearance of asexual parasites from the blood on or before day 7 after treatment, and
- Recurrent asexual stage parasitemia on or before day 42.

Assessment and Reporting of Parasitologic Outcomes

Based on the parasitologic data, the PI and one physician colleague (both blinded to the treatment the patients received) will assess the parasitologic outcomes for each of the participants. Those data will then be summarized by the subject's study numbers and returned to the study statistician who will place the data in groups by study arm (retaining blindedness by using Arm 1 and Arm 2 to identify the study arm rather than AQ-13 and Coartem) before the data are tested for differences and presented to the DSMB.

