Times to recrudescence and reinfection will be analyzed using life tables, and compared using the log rank test. Cox regression will be used to compare multiple (multivariate) predictors of times to recrudescence and reinfection. Pharmacokinetic parameters will be examined for AQ-13 doses and compared to data from the Phase 1 studies, as appropriate. **Using the same protocol as in the Phase 1 study [11], the relatedness of adverse events (AEs) to study drugs will be classified independently by two blinded physicians according to the definitions in section 8.3 on page 30 as unknown, not related, unlikely to be related, or possibly, probably or definitely related to the study drugs, based on temporal relationships and biological plausibility.** The frequencies of AEs will be compared between AQ-13 and Coartem using Pearson Chi-square. Because more than one AE may occur in an individual patient, the proportion of patients receiving AQ-13 with AEs will be compared with Coartem using Chi-square or the Fisher Exact test. The severity of AEs will be classified using the recent FDA Guidance for Healthy Adult and Adolescent Volunteers in Preventive Vaccine Trials [23], and the severity of AEs across the study arms will be compared using Chi-square. QT interval corrections for heart rate (QTc) will be made using both Bazett's and Fridericia's formulas [41-42]. Within-patient maximum changes from baseline will be assessed using the Wilcoxon test for paired observations. Between-group QT interval changes will be compared using ANOVA or Kruskal-Wallis.

HYPOTHESES BEING TESTED.

The primary hypothesis is that the efficacy of AQ-13 for uncomplicated *P. falciparum* malaria is similar to

that of Coartem - based on a non-inferiority margin of 15%. That is, that AQ-13 will produce a cure rate within 15% of the Coartem control (standard). The secondary hypothesis is that AQ-13 will have safety profiles in subjects with uncomplicated malaria comparable to those for AQ-13 in healthy volunteers [11].

EXPECTED OUTCOMES.

Our preliminary (previous) studies have shown that AQ-13 is:

- *active in vitro* against CQ-resistant and multi-resistant *P. falciparum* [8-9],
- *active in vivo* against CQ-resistant *P. falciparum* in the squirrel monkey model of human infection with CQ-resistant *P. falciparum* (enclosed Figures 1 and 2 in the Appendix), and
- *safe in human subjects* based on Phase 1 studies recently performed in New Orleans [11].

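### Parasite clearance time is compared between arms with no covariate named; pre-specifying log admission parasite density costs nothing and may add up to about 17 points of power

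*Combined protocol and SAP*

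**What the plan says.** Section 7.1.2 makes parasite clearance time a secondary outcome, measured "from the initiation of treatment to the first of 2 successive negative smears". Its only analysis statement is in Table 7 (section 10.1): "Time to parasite Clearance, Recrudescence or Reinfection (between groups) Kaplan-Meier, Cox Hazard". The text of section 10.3 does not mention clearance time. Its one sentence on multi-predictor models reads "Cox regression will be used to compare multiple (multivariate) predictors of times to recrudescence and reinfection".

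Section 6.2.1 admits men with "2,000 to 99,999 asexual parasites per" microlitre; the upper limit is also exclusion criterion 2 in section 5.2. Section 7.2.1 counts parasites on smears "containing a minimum of 300 white blood cells and multiplying the number of asexual parasites observed by 25", on the basis of a "white blood cell count of 7,500 white cells per" microlitre. Section 10.4 randomises in permuted blocks of 4 and 6 and states no stratification by density.

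The smear interval is given in two ways. Section 7.2.1 has smears "continuing twice daily (every 12 hours) until two successive smears are negative". Flow Chart 3 in section 4 has "Repeat Daily Blood Smears (days 1 through 7" (days inclusive).

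**The concern.** Clearance time is the time for the admission parasite load to fall to a level where the smear is negative. On that definition a man who starts higher takes longer at the same rate of decline, whichever drug he receives. Entry density may vary widely, and as written neither the randomisation nor the analysis takes account of it.

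Two things are at stake. Spread in clearance time that comes from the starting count stays in the comparison as noise. And with about 30 men per arm, the arms can differ in mean density by chance, which an unadjusted comparison cannot separate from a difference between drugs.

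The covariate is already available. The count decides eligibility and is the denominator of the day-3 criterion (below 25% of the admission value). Events are plentiful too: cure requires clearance by day 7, so an expected cure rate of 95% implies that at least 95% of men clear by then.

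**Working it through.** The documents give no power, effect size or variance for clearance time, so there is no planned figure to reproduce beyond the counting rule. That rule is consistent: 7,500 / 300 = 25, so one parasite seen corresponds to 25 per microlitre.

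**1. Entry range.** 99,999 / 2,000 = 50-fold.

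**2. Effect of density on clearance time.** Assume log-linear decline at rate k with no lag (the documents state no such model). Then T = ln(P0 / 25) / k, and k cancels in a ratio.

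- Lowest entry density: ln(2,000 / 25) = 4.38
- Highest entry density: ln(99,999 / 25) = 8.29
- Ratio of the extremes: 8.29 / 4.38 = 1.89 (1.74 for a limit of 10 per microlitre, 2.06 for 50)
- 75th versus 25th percentile, if density is log-uniform: (4.38 + 0.75 × 3.91) / (4.38 + 0.25 × 3.91) = 7.32 / 5.36 = 1.36

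**3. Chance imbalance.** For log-uniform density, the SD of ln density is ln(50) / √12 = 1.13. At 28 per arm the SE of the difference in means is 1.13 × √(2/28) = 0.30. About 1 trial in 20 would have an imbalance of at least 1.96 × 0.30 = 0.59. The mean log distance to the limit is (4.38 + 8.29) / 2 = 6.34, so that imbalance shifts mean clearance time by 0.59 / 6.34 = 9% with no drug difference.

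**4. Power.** Clearance times were simulated from the model in step 2 with between-man variation in k and read at the next smear. Treatment was tested by Cox regression at two-sided 0.05, with and without log density. There were 600 simulated trials per scenario, or 400 where marked *. Density was log-uniform and smears 12-hourly unless stated. Effect size, variance and density distribution are all assumptions. Narrower density means a truncated lognormal with median parameter 8,000 and log SD 0.8.

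| Per arm | Assumed effect | Spread of k | Other | Unadjusted | Adjusted |
|---|---|---|---|---|---|
| 28 | 20% slower | CV 20% | | 77% | 94% |
| 28 | 20% slower | CV 30% | | 59% | 74% |
| 28 | 20% slower | CV 40% | | 42% | 50% |
| 28* | 20% slower | CV 50% | | 32% | 36% |
| 28* | 20% slower | CV 30% | narrower density | 53% | 64% |
| 28* | 20% slower | CV 40% | narrower density, daily smears | 40% | 42% |
| 28* | 40% slower | CV 30% | | 99.8% | 100% |
| 28* | 40% slower | CV 40% | | 97% | 99% |
| 33 | half-life 25% longer | log SD 0.15 | | 90% | 99.8% |
| 33 | half-life 25% longer | log SD 0.30 | | 58% | 74% |
| 33 | half-life 25% longer | log SD 0.30 | daily smears | 48% | 57% |
| 33 | half-life 25% longer | log SD 0.50 | | 37% | 42% |
| 33 | half-life 40% longer | log SD 0.30 | | 92% | 97% |
| 33 | half-life 40% longer | log SD 0.50 | | 63% | 65% |

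The gain runs from 0.2 points (99.8% to 100%) to 17 points (77% to 94%). Each power figure carries a Monte Carlo standard error of up to √(0.25 / 600) = 2.0 points, or √(0.25 / 400) = 2.5 points where marked *, so the smallest gains may be little or nothing. With no drug effect (33 per arm, log SD 0.30) both tests rejected in 4.5% of trials.

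In the 33-per-arm runs, density explained about 7% to 43% of the variance of log clearance time.

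**The case against.** The plan is silent rather than opposed. Table 7 already lists Cox for this endpoint and gives its tests in outline only. Clearance shares its line with recrudescence and reinfection, so the sentence in section 10.3 may be loosely worded and not a choice to withhold adjustment. A reader might infer that the plan decided against adjustment; the documents do not show that. What stands is that no covariate is pre-specified, which leaves the choice open until the data have been seen.

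A reader might also infer that density will nearly double clearance time in this trial, or that it is the main determinant of it. Neither is supported. The 1.9-fold figure compares the two extreme eligible men under an assumed model, the entry window is not an observed spread, and the documents rank no determinants.

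The unadjusted test keeps its type I error. A chance imbalance in density is sampling error already inside the nominal 5%, so the planned test is not biased. Adjustment still helps the reading of the one trial that is run.

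Last, log-linear decline does not imply proportional hazards, so Cox is one option among several. That is fair. It is proposed because the plan already names it.

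**Conclusion.** The point holds as an improvement that costs nothing, not as an error that invalidates a result. The planned comparison of clearance time omits a covariate that is measured in every man and that, by the endpoint's own definition, bears on the outcome. The test as written is valid but loses precision and does not account for chance imbalance in density.

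The size depends on inputs that the documents do not give. Across the scenarios the power gain was from under 1 to about 17 percentage points. It is least when the drug effect is large, between-man variance is high, density is narrow or smears are daily. The direction is well supported; the magnitude is not. Sample size and the non-inferiority decision rest on cure, so the primary conclusion is unaffected.

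**What to change.** In Table 7 and section 10.3, pre-specify that the between-arm test of parasite clearance time is a Cox model with treatment and log10 admission parasite density. Keep the Kaplan-Meier curves for display and report the unadjusted comparison as supportive. State that the adjusted hazard ratio compares men of the same admission density.

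Reconcile the smear frequency in Flow Chart 3 (section 4) with that in section 7.2.1, because the interval sets the resolution of this endpoint.

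The analysis change costs one sentence and needs no new data, provided it is made before the data are compared by arm.
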